### 8.1.2 Secondary study parameters/endpoints

The most important secondary outcome measures will be QoR and QoL. QoR will be scored using the QoR-15 questionnaire (MCID 8) at baseline, POD 0-3 and at 4 weeks' follow-up. QoL will be measured using the EORTC QLQ-C30, which has previously shown to be of value in PSP patients when comparing VATS versus thoracotomy (26). The questionnaire will be administered at baseline and at 4 weeks, 3 months and 1 year postoperatively.

Additional secondary outcome measures:

1. Number of postoperative days having a urinary catheter
2. Postoperative morbidity during the first 30 days, defined by the Clavien Dindo classification
3. Duration of postoperative chest tube drainage
4. Postoperative pain scores at rest and during mobilization/coughing during POD 0-4 and at 4 weeks, 3 months and 1 year follow-up
5. Cumulative use of postoperative additional analgesics and opioids during POD 0-4 and opioid use at 4 weeks follow-up
6. Daily degree of patient mobility (scale: in bed (1), in the chair (2), to the toilet (3), outside the patient's hospital room (4)) during POD 0-4
7. Health status scored by the EQ-5D tool at baseline, POD 0-3, after 1 month, after 3 months and after 1 year follow-up
8. Patient satisfaction using the 5-point Likert scale during POD 0-4.
9. Cumulative use of additional chest X-rays and/or CT-scans (including reason)
10. Cost-effectiveness and cost-utility from a health care perspective using adjusted iMTA questionnaires, the DMCQ and PCQ, at 4 weeks, 3 months and 1 year postoperatively.
11. The impact on the national health care budget from governmental, insurer and provider perspectives. The planning horizon of the budget impact analysis will be the first 4 full calendar years following study closure.

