#### **5.6 Follow up**

After surgery, patients will be admitted to the ward. After chest tube removal and TEA removal (in case this is performed), patients may be discharged in case of sufficient pain control (NRS  $<4$ ) with oral pain medication and sufficient self-care. In case patients fulfil the discharge criteria but remain admitted to the hospital, the reasons will be noted. During hospital stay patients will complete a diary for at least POD 0-3 (for pain scores, quality of recovery and EQ-5D health status). In case of discharge before POD 3, patients will complete their diary at home for at least POD 0-3. After 4 weeks, patients will be seen at the outpatient clinic in order to actualize postoperative morbidity, pain, QoR, QLQ-C30 and EQ-5D-5L. Also, diaries will be collected. After 3 months and 1 year patients will be contacted by telephone through the outpatient clinic to actualize for ipsilateral pneumothorax recurrences, to evaluate the presence of thoracic pain with pain scores and the QLQ-C30 and EQ-5D-5L will be registered. For cost-effectiveness analyses adjusted iMTA questionnaires, the Dutch Medical Consumption Questionnaire (DMCQ) and Productivity Cost Questionnaire (PCQ), will be completed at baseline, 1 month, 3 months and 1 year after surgery.

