## 10.2 Secondary study parameters

1. QoR-15 pre-operatively as baseline score, at POD0-3 and at 4 weeks' follow up. Questionnaire scores (maximum 150 points) will be presented as means with standard deviation or median with interquartile range depending on distribution. Comparisons will be made using the student's t-test or Mann Whitney U test.
2. QoL will be measured using the EORTC QLQ-C30 at baseline and at 4 weeks, 3 months and 1 year postoperatively. Questionnaire scores will be presented as means with standard deviation or median with interquartile range depending on distribution. Comparisons will be made using the student's t-test or Mann Whitney U test.
3. The duration of having a urinary catheter will be presented in days starting from POD 0. Results will be presented as means with standard deviation or median with interquartile range depending on distribution. Comparisons will be made using the student's t-test or Mann Whitney U test.
4. Postoperative morbidity during the first 30 days according to the Clavien-Dindo classification system. Results are presented as the number of patients divided into categories (Grade I to V) according to the Clavien-Dindo classification. These proportions will be compared between the 3 randomization groups by chi square test or Fisher's exact test, based on intention to treat.
5. Total duration of postoperative chest tube drainage in days will be presented as means with standard deviation or median with interquartile range depending on

- distribution. Comparisons will be made using the student's t-test or Mann Whitney U test.
6. Postoperative pain scores at rest and during mobilization during POD 0-4 and at 4 weeks, 3 months and 1 year follow-up will be presented as means with standard deviation or median with interquartile range depending on distribution. Comparisons will be made using the student's t-test or Mann Whitney U test.
  7. Cumulative use of postoperative additional analgesics and opioids during POD 0-4 and at 4 weeks follow up will be presented in the measure of milligrams (mg) using means with standard deviation or median with interquartile range depending on distribution. Comparisons will be made using the student's t-test or Mann Whitney U test.

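### Four secondary outcomes run to POD 4, but no post-discharge source is stated to that day, so capture can differ by arm; opioid use is also reported in plain mg

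*Protocol*

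**What the plan says.** Protocol section 8.1.2 sets four secondary outcomes over POD 0-4:

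- Pain: "Postoperative pain scores at rest and during mobilization/coughing during POD 0-4".
- Analgesics: "Cumulative use of postoperative additional analgesics and opioids during POD 0-4 and opioid use at 4 weeks follow-up".
- Mobility: a four-level daily scale whose top level reads "outside the patient's hospital room (4)) during POD 0-4".
- Satisfaction: "Patient satisfaction using the 5-point Likert scale during POD 0-4".

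Table 1 in section 8.3 marks all four from the day of surgery to POD 4, with no distinction between patients in hospital and patients at home.

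Section 5.6 describes the diary: "During hospital stay patients will complete a diary for at least POD 0-3 (for pain scores, quality of recovery and EQ-5D health status". After early discharge it continues: "In case of discharge before POD 3, patients will complete their diary at home for at least POD 0-3". Section 8.3 has pain scored three times daily for four days, and QoR-15 and EQ-5D completed daily on POD 0-3. Section 5.5 has all analgesics registered in the CRF and does not mention doses taken at home. Section 10.2 item 7 says that cumulative use "will be presented in the measure of milligrams (mg".

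**The concern.** Patients leave hospital on oral pain medication (section 5.6), so analgesic use can continue after discharge. The next scheduled contact is the 4-week visit. If the text is followed literally, three of the four outcomes have no stated source once the patient is home, and pain has none on POD 4.

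This would be a small loss if discharge time were unrelated to treatment, but discharge time is what both interventions are meant to change. Incomplete capture would then fall unevenly across arms. For opioids, the uneven part could run against the direction the protocol predicts: section 11.4 expects PVB patients to have more episodes of NRS 4 or above and to need more morphine. An analysis plan written later cannot recover data that were never collected.

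**Working it through.** **1. Outcome windows against the stated post-discharge source**

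| Outcome | Window (8.1.2, Table 1) | Stated source after discharge | Unsecured days at home |
|---|---|---|---|
| Pain at rest and on movement | POD 0-4 | Diary, required to POD 3 | POD 4 |
| Analgesic and opioid use | POD 0-4 | None stated; CRF only | All days after discharge |
| Mobility | POD 0-4 | None stated; scale worded for a hospital room | All days after discharge |
| Satisfaction | POD 0-4 | None stated | All days after discharge |
| QoR-15, EQ-5D | POD 0-3 | Diary, POD 0-3 | None |

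Four diary days starting at POD 0 end at POD 3. The text of section 8.3 and its own Table 1 therefore differ on POD 4 pain.

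**2. Does time in hospital differ by arm?** Discharge requires removal of the chest tube and, where placed, of the TEA (section 5.6). The tube may come out from 4 hours in the early arms (5.3) but not before POD 3 in usual care (5.2). The TEA catheter stays at least 2 days (8.3), while PVB uses no catheter (5.3). Both factors therefore shift discharge. Section 4.4 expects mean LOS of 3.9 against 5.3 days, and section 5.3 cites discharge 1.0 day earlier with locoregional analgesia.

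The plan's LOS figure reproduces. With difference 1.4, SD 4.5, two-sided alpha 0.05 and 80% power, n = 2 × (1.96 + 0.84)² × 4.5² / 1.4², which gives 163 per group. The t-based version gives 163.1, so 164. With 10% drop-out, 164 / 0.9 = 183 per group, or 366 in total. This figure is not in dispute.

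**3. How many patients might be home by POD 4?** (Assumption: lognormal or gamma LOS with the section 4.4 means, SD 3.0 to 4.5, and LOS under 4 days read as home before POD 4.) The share is about 61-69% with early removal and 39-49% with late removal. This is rough: the same curves place 21-38% of late-removal patients under 3 days, which the POD 3 rule should largely prevent.

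**4. What would ward-only recording capture?** (Assumption: no doses are recorded after the day of discharge, and the recorded doses are summed.) With flat daily use, discharge on POD d captures (d + 1)/5. With use declining 5:4:3:2:1, the denominator is 15.

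| Discharge | Flat | Declining |
|---|---|---|
| POD 1 | 2/5 = 40% | 9/15 = 60% |
| POD 2 | 3/5 = 60% | 12/15 = 80% |
| POD 3 | 4/5 = 80% | 14/15 = 93% |
| POD 4 or later | 100% | 100% |

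With identical true use, POD 1 against POD 3 shows an apparent reduction of 1 − 40/80 = 50% (flat) or 1 − 9/14 = 36% (declining). At the expected means, a stay of 3.9 days falls between the POD 3 and POD 4 rows and 5.3 days lies beyond POD 4. The apparent reduction there is 0-20% (flat) or 0-7% (declining).

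**5. Units.** The protocol allows an opioid in the epidural solution and oral or intravenous opioids if rescue of the epidural fails (5.2), opioids in recovery (5.4) and oral oxycodone (5.5). Drug and route can differ systematically between TEA and PVB, so a plain mg total is not a common scale.

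**The case against.** The strongest reply is that the protocol is silent on the method, which is not the same as having none. Table 1 schedules opioid dosage, mobility and satisfaction on POD 4 for everyone, and opioid dosage again at later contacts. Section 5.5 registers all analgesics in the CRF. The diary duration is a minimum and the diary is collected at 4 weeks. The CRF, the diary and the data management plan are not at hand. This stands in part: a reader may not conclude that home doses go unrecorded or that early-discharge arms will show less opioid use, only that this can happen. If incomplete totals are set to missing instead of summed, the problem becomes informative missingness.

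Other limits also stand:

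- A 50% false reduction is tempting to quote, but it needs flat use, no home recording and a two-day gap, against an expected mean difference of 1.4 days.
- The primary pain endpoint might seem to be affected. It is not: it covers POD 0-3, and the diary follows pain home to POD 3.
- The mobility scale might seem to have no value for someone at home. A discharged patient could be coded to the top level; the protocol does not say so.
- Opioid sparing might be taken as part of the argument for PVB. The protocol argues comparable analgesia with fewer epidural side-effects, and section 11.4 expects more morphine.
- Nothing says that epidural opioid is summed into additional use.

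Conversion to equivalents is often left to an analysis plan. Here, however, section 10.2 names the unit, so the protocol itself has fixed a metric that does not compare well between arms.

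**Conclusion.** The mismatch is real. No stated mechanism secures POD 4 pain after discharge, nor analgesic and opioid use, mobility or satisfaction on any of these days after discharge. Because time under observation differs by arm by design, the resulting gaps can depend on treatment.

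The size cannot be determined from the document. It rests on what is recorded at home, how incomplete totals are handled and how use changes over time; the shares above are illustrations under stated assumptions. A firm claim that the results will be spurious is not supported.

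The unit for opioids is a second, smaller weakness: oral, intravenous and possibly epidural opioids of different potency are added in mg.

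Only secondary outcomes are touched. The primary pain endpoint, QoR, LOS and the sample size are not affected. Severity is minor to moderate.

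**What to change.** - Add analgesic and opioid intake (drug, dose, route), satisfaction and a mobility item usable at home to the diary. Require the diary to POD 4 for every patient, wherever they are. Alternatively, cut these four outcomes to POD 0-3, with the same additions to the diary.
- Align sections 5.6, 8.1.2, 8.3 with Table 1, and 10.2, so that window, content and source agree.
- In section 10.2 item 7, report opioids as oral morphine equivalents, with any epidural opioid shown separately.

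The cost is about one extra diary page per day, some CRF wording and a small patient burden. No sample size or primary analysis changes.

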  8. The degree of mobility defined as an ordinal scale (in bed (1), in the chair (2), to the toilet (3), outside the patient's hospital room (4)) and will be presented as the number of patients per category for POD 0-4. Comparison between the three randomization groups will be made using the Chi square test or Fisher's exact test.
  9. Health status scored by the EQ-5D tool at baseline, POD 0-3, after 4 weeks, 3 months and 1 year follow-up. Questionnaire scores will be presented as means with standard deviation or median with interquartile range depending on distribution. Comparisons will be made using the student's t-test or Mann Whitney U test.
  10. Patient satisfaction using the 5-point Likert scale (not at all satisfied, slightly satisfied, neutral, very satisfied and extremely satisfied) will be presented as the number of patients per category for POD 0-4. Comparisons between the three randomization groups will be made using the Chi square test or Fisher's exact test.
  11. Cumulative use of additional chest X-rays and/or CT-scans will be documented including reasons. Evaluation of the reasons of additional use will take place using descriptive statistics. Also, the amount of additional imaging will be compared between the three randomization groups using the Chi square test or Fisher's exact test.
  12. A cost effectiveness and cost-utility analysis from a health care and societal perspective of both chest tube drainage and analgesic techniques will be performed. The time horizon is 1 year, the period it takes to resolve the aftermath of a pneumothorax (and possible recurrence) in this mostly young and healthy population. Whereas safety margins regarding recurrence (interim analyses by our DSMB) as well as upper margins for non-inferiority regarding pain are in place, we expect that the reduction in LOS and improved QoR during the POD 0-3 generate the economic benefits. Hence, cost-effectiveness and cost-utility analyses are done with total costs, out-of-hospital days during follow-up, total QoR score and QALYs. Incremental ratios

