are calculated for the extra costs per additional day out of hospital, per unit increase in QoR score point and per additional QALY. Sensitivity analyses are done to account for sampling variability (following bootstrapping) and plausible ranges in unit costs of surgical and anaesthesiologic treatments. Cost-effectiveness acceptability curves are drawn, showing the probability of early chest tube removal or single-shot PVB sedation being cost-effective at various levels of willingness-to-pay per QALY up to 50,000 euros. Subgroup analyses are done for patients treated by pleurectomy or chemical pleurodesis and for patients above or below under 40 years of age. Regarding cost analysis, the evaluation includes health care, patient/family, and other costs. Health care costs include the costs of all analgesic procedures, therapeutic (repeat) interventions, medication, admissions, day care treatments, specialist consultations, and out-of-hospital care (like general physician, physiotherapy etc.). Out-of-pocket expenses include the costs of health-related travel, over-the-counter medication, informal help, etc. Other costs like productivity losses reflect costs of sick leave from work or lowered efficiency while at work. Data on resource use are gathered with clinical report forms, hospital information systems, and patient questionnaires. Patients complete the DMCQ and PCQ, adjusted to the study setting and extended, at POD 30, 3 months and 1 year after surgery. Micro-costing (general anesthesia, surgical and anaesthesiologic equipment, procedure duration, involved personnel, and overhead) is done in participating centers to derive real unit costs of the index interventions. The most recent Dutch manual on costing in health care or passer-by tariffs are applied to other health care resources. The friction costs method is applied to derive the costs of lost productivity. Out-of-pocket expenses are based on self-report. After price-indexing all costs will be expressed in Euros with base-year 2026.

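### The economic outcome is defined from a health care perspective but analysed from two perspectives, and the baseline cost questionnaire is missing from both the definition and the analysis text

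*Protocol*

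**What the plan says.** Cost-effectiveness and cost-utility are among the secondary objectives in Protocol section 2. Section 8.1.2, item 10, gives the outcome, its instruments and its times as "Cost-effectiveness and cost-utility from a health care perspective using adjusted iMTA questionnaires, the DMCQ and PCQ, at 4 weeks, 3 months and 1 year". Section 5.6 spells out the PCQ as a questionnaire on productivity costs.

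The analysis text in section 10.2, item 12, is wider: "A cost effectiveness and cost-utility analysis from a health care and societal perspective of both chest tube drainage and analgesic techniques will be performed". On what enters the ratios it says that "cost-effectiveness and cost-utility analyses are done with total costs, out-of-hospital days during follow-up, total QoR score and QALYs". On the cost components it says: "Regarding cost analysis, the evaluation includes health care, patient/family, and other costs". Lost work is priced too: "The friction costs method is applied to derive the costs of lost productivity". The same item lists the patient cost questionnaires at postoperative day 30, 3 months and 1 year.

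The collection sections add a time point. Section 5.6 says the cost questionnaires "will be completed at baseline, 1 month, 3 months and 1 year after surgery". Section 8.3 has a baseline iMTA questionnaire completed around informed consent, and the iMTA row of Table 1 is marked at baseline.

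Section 10.2, item 13, takes the strategy found most efficient, compares it with epidural plus late tube removal, and values the difference in specialist medical care costs.

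**The concern.** A health care perspective leaves out productivity losses and, ordinarily, patient and family expenses. A societal perspective includes them. The two have different cost numerators, so they can give different incremental ratios, different acceptability curves and, with four arms, a different ranking of strategies. The protocol defines the outcome by one and analyses it by both, and it does not say which one leads.

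Item 10 also does not fit itself: it restricts the perspective to health care while naming an instrument that serves productivity costs.

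The baseline questionnaire is a separate matter. It is a burden on patients, and its data are useful for adjusting cost comparisons, but the two sections that say what is measured and analysed for this outcome do not mention it. At stake are a clear definition of a stated objective and some precision in the cost difference. The primary outcomes, the sample size and the recurrence rule are not touched.

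**Working it through.** The protocol states no figure to reproduce, so the main check is a comparison of its sections. Four weeks, one month and postoperative day 30 are read as the same visit.

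| Place | Perspective | Cost scope | Baseline listed? |
|---|---|---|---|
| 8.1.2, item 10 | health care | not stated, but the PCQ is named | no |
| 10.2, item 12 | health care and societal | health care, patient/family, other, including lost productivity | no |
| 5.6 | none stated | DMCQ and PCQ | yes |
| 8.3 | none stated | adjusted iMTA questionnaire | yes |
| Table 1 | none stated | iMTA row, labelled iMCQ and iPCQ | yes |

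**Perspective.** The mismatch is between 8.1.2 and 10.2. The collection sections state no perspective.

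**Time points.** The split runs differently: the outcome and analysis sections agree with each other in omitting baseline, and the three collection sources include it.

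**Selection for item 13.** The cost basis of the budget impact is stated. The perspective under which the most efficient strategy is chosen is not.

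**Illustration of the perspective difference (prices assumed).** The only document input is the 1.4-day difference in length of stay from section 4.4.
- Health care saving at 450 to 750 euros per bed day: 1.4 × 450 = 630 and 1.4 × 750 = 1,050 euros per patient.
- Extra societal saving if every saved day is a day worked, at 200 to 350 euros: 1.4 × 200 = 280 and 1.4 × 350 = 490 euros.
- Relative to the health care saving: from 280/1,050 = 27% to 490/630 = 78%.
- If return to work is unchanged, the extra saving is 0.

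The range therefore runs from 0% to 78% on assumed prices, which means that the document does not fix a size.

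**Illustration of the precision issue (work share and loss assumed).** Section 4.4 gives 164 per tube-removal group. With a share p in paid work, the standard error of the chance difference in that share is √(p(1 − p) × 2/164).
- At p = 0.6: √(0.24 × 2/164) = 0.054.
- The largest possible value, at p = 0.5, is √(0.25 × 2/164) = 0.055.
- At an assumed productivity loss of 3,000 euros per working patient, 0.054 × 3,000 = 162 euros per standard error. The figure scales in proportion to the assumed loss.

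This is random variation between groups with expectation zero, part of which baseline adjustment can remove.

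**The case against.** The strongest reply is that item 12 already commits to both perspectives. The health care result promised in 8.1.2 is therefore contained in the analysis and not displaced. No success rule hangs on either result, because the plan is for acceptability curves over a range of willingness to pay up to 50,000 euros per QALY. Assigning curves to perspectives and choosing covariates is commonly left to a SAP, which is not at hand. The outcome is the tenth in the list of additional secondary measures.

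Most of this stands, and it limits the point. A reader might infer that the economic conclusion can be drawn from whichever perspective looks better. The text does not support that, since both are to be done. A reader might also infer that the baseline data enter no cost analysis. The sections list time points and are silent on use; silence does not exclude adjustment. Nor does the missing baseline produce a second cost result; only the perspective mismatch could. Item 13 might seem to have no defined costs, but it names specialist medical care costs, which is narrower than item 12's health care costs and clear as written.

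What the reply does not remove is the conflict between two statements in the same protocol. A SAP can add detail, but whichever perspective wording it follows, it departs from one section. The choice of perspective for selecting the most efficient strategy also remains open.

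**Conclusion.** The point holds as a minor inconsistency in a secondary outcome. The definition names one perspective and the analysis two. The productivity questionnaire does not fit the definition, the perspective that selects the strategy for item 13 is unstated, and the baseline questionnaire is collected but absent from the outcome and analysis text.

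Its size in euros cannot be derived from the protocol; the figures above rest on assumed prices, employment and productivity loss, and the extra societal saving may be nil. It would be tempting to call chance imbalance in paid work a bias. It is not: in a randomised comparison it is a loss of precision, and the planned bootstrap would already reflect it. Nor does the text support the societal perspective as the right base case; 8.1.2 names health care, so the choice belongs to the sponsor. Adjustment for baseline data is a worthwhile gain from data already scheduled, and its absence is not an error in itself.

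**What to change.** - In 8.1.2, item 10, write: *from a health care and a societal perspective, at baseline, 4 weeks, 3 months and 1 year*.
- In 10.2, item 12, add baseline to the list of questionnaire times.
- In the same item, report each perspective with its own incremental ratios and acceptability curve. State in advance which perspective is the base case (the sponsor's choice) and that it selects the most efficient strategy for item 13.
- Adjust the bootstrapped cost difference for the baseline cost and work data, and for the randomisation strata (age around 40 years and the hospital's pleurodesis technique).
- Leave the wording of item 13 on specialist medical care costs as it is.

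The cost is a change of wording in two sections and a regression step within the bootstrap. No new data are needed, because every questionnaire involved is already scheduled.
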